### 4.4.2 Blinding

The study treatment is prescribed openly. Blinding within this study is not planned.

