## 9.2 Interim analysis

One formal Interim analysis to assess the primary and secondary endpoints of efficacy is planned when the population of patients with available primary efficacy endpoint data is at least 240 patients (120 patients in each group treatment: the main group is Ferrum Lek® (iron (III) hydroxide polymaltosate) and the reference group MALTOFER® (iron (III) hydroxide polymaltosate). Safety and Efficacy will be assessed for all patients who received at least one dose of the randomized treatment at the time of the interim analysis. Based on the results of the interim analysis of the primary and secondary statistical endpoints of the efficacy and safety of the study Sponsor may decide to stop the study if study endpoints have been met as per protocol based on the results of interim analyses or sample size might be recalculated using results of interim analyses.

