- 12) Non-inferiority margin is 5 g/L.
- 13) The significance level (two-sided, in accordance with FDA recommendations) is 95%, which corresponds to the type I one-sided error 0.05.
- 14) Power of the study is 80%, which corresponds to the type II error 0.20.
- 15) Statistical hypotheses evidence of a non-inferior efficacy:

- 16) The ratio between the study and control group sizes is 1:1
- 17) Interim analysis will be performed at 70% of the total sample size
- 18) O'Brien-Fleming alpha-spending function will be used with 80% power for efficacy boundary that will correspond to the following critical values for t-test: 2,628 for interim analysis (corresponds to p=0,005) and 1,976 for final analysis (corresponds to p=0,0245);

Calculation was performed using the clinfun package of Microsoft R Open software (available at https://mran.microsoft.com – Microsoft R Application network), that uses the group sequential design approach for the calculation of fixed sample sizes for the interim and final analysis. According to the output from the clinfun package, 143 subjects per group (286 subjects in total) should complete the study in order to confirm non-inferiority. 200 (100 per group) subjects should have evaluable data to perform interim analysis. Taking 15% withdrawal rate into account, one need to randomize 336 subjects (168 subjects per group). Taking 30% screening failure rate, up to 480 subjects should be screened to achieve target randomization.

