All data provided for the evaluation will be integrated into the final clinical study report which will describe the methodology for conducting statistical analysis, as well as clinical conclusions regarding efficacy and safety.

The CS report will be prepared by the CRO in cooperation with the Sponsor. The principal investigator of each study site will receive a copy of the Report for review and subsequent signing. The structure and content of the Report will generally comply with the requirements of the ICH E3 guidelines, as well as applicable local regulatory requirements.

If recalculation of the sample size using the results of the interim analysis is necessary, Report on the interim analysis results will be generated, it will be submitted to the regulatory authority of the Russian Federation with a view to obtaining permission to continue the clinical study involving an increased number of patients.

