9.2. Other safety endpoints

No other safety endpoints are foreseen in this study.

10. Exploratory analysis

In the course of this study, exploratory analysis is not envisaged.

11. Interim analysis

One interim analysis is planned to assess the primary and secondary efficacy endpoints when a group of patients with available data on the primary endpoint will include at least 200 subjects [100 patients in each treatment group: in the main treatment group of patients taking Ferrum Lek[®] (iron (III) hydroxide polymaltosate complex) and in the control group of patients taking MALTOFER[®] (iron (III) hydroxide polymaltosate complex]. Safety and efficacy will be assessed in all patients who have received at least one dose of randomized therapy at the time of the interim analysis. Based on the results of the interim analysis of the primary and secondary statistical endpoints of efficacy and safety, the Sponsor may decide to discontinue the study if the endpoints of the study are achieved in accordance with the protocol based on the results of the interim analyses or the sample size can be recalculated using the results of the interim analysis.

STATISTICAL ANALYSIS PLAN

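### Sample size may be recalculated from the open-label interim comparison with no rule, cap or matching final test, so the implied one-sided 2.5% error is not guaranteed

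*Protocol*

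**What the plan says.** **Recalculation.** Protocol 9.2 plans one interim analysis of the primary and secondary efficacy endpoints. The sponsor may then stop, "or sample size might be recalculated using results of interim analyses". SAP 11 agrees that "the sample size can be recalculated using the results of the interim analysis". Protocol 12 shows the intended direction: an interim report goes to the Russian regulator with a view to "obtaining permission to continue the clinical study involving an increased number of patients". The synopsis text on the interim analysis mentions stopping only. On masking, Protocol 4.4.2 states: "Blinding within this study is not planned".

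**Final test.** Protocol 9.1.2 and SAP 8.1 use an ANCOVA confidence interval for the difference in LS means, compared with 5 g/L. SAP 8.1 sets the confidence level by whether the look is interim or final, and refers to SAP 2.3. The critical values in SAP 2.3 and Protocol 9.3 are 2.628 at the interim and "1,976 for final analysis (corresponds to p=0,0245"). Protocol 9.1.2 still gives a plain 95% interval.

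**Error level.** Protocol 9.3 says: "The significance level (two-sided, in accordance with FDA recommendations) is 95%, which corresponds to the type I one-sided error 0.05". SAP 2.3 repeats this.

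**Interim size.** The synopsis text on the interim analysis and Protocol 9.2 say 240 patients (120 per arm). Protocol 9.3, SAP 2.3 and SAP 11 say 200 (100 per arm), planned as 70% of the total.

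**The concern.** The pair 2.628 and 1.976 controls error for a trial whose second stage has a fixed size. If that size is chosen after seeing the treatment difference, the statistic on all data no longer has the null distribution that 1.976 assumes. Enlarging after a poor interim dilutes the bad first stage and gives the product a better chance of crossing.

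This is the trial's only confirmatory test; Protocol 9.1.3 makes the secondary efficacy analyses exploratory. The error runs towards declaring non-inferiority for a product that is truly worse by the full 5 g/L. It is hard to repair credibly once open-label interim results have been seen.

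**Working it through.** **Inputs.** Margin 5 g/L, SD 15 g/L, true difference 0, power 80%, 143 per arm, critical values 2.628 and 1.976 (Protocol 9.3, SAP 2.3). Interim n1 = 100 or 120 per arm. Caps on the final size are assumptions: 215 and 286 per arm are about 1.5 and 2 times 143.

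**1. Which error level the design uses.** For a fixed design, n = 2 × 15² × (z_alpha + 0.842)² / 5² = 18 × (z_alpha + 0.842)².
- One-sided 0.025: 18 × (1.960 + 0.842)² gives 142 per arm.
- One-sided 0.05: 18 × (1.645 + 0.842)² gives 112 per arm.

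The planned 143 fits 0.025. With the two looks (100 of 143 is a fraction of 0.70), power at 143 is 80.25%, so the plan's figure is reproduced. The implied level is one-sided 2.5%, not the stated 0.05.

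**2. No recalculation.** Let z1 be the interim statistic for non-inferiority, standard normal when the product is worse by exactly the margin. For second-stage size n2 per arm, the chance of crossing at the end given z1 is

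A(z1, n2) = 1 − Phi[(1.976 × sqrt(n1 + n2) − sqrt(n1) × z1) / sqrt(n2)].

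Total error = P(z1 > 2.628) + the integral of A over z1 < 2.628, with P(z1 > 2.628) = 0.0043.
- n1 = 100, n2 = 43: 0.0250.
- n1 = 120, n2 = 23: 0.0243.

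**3. Why a data-driven n2 matters (n1 = 100).**
- z1 = 1.0. Final 143: (1.976 × 11.958 − 10)/6.557 = 2.08, so A = 0.019. Final 286: (1.976 × 16.912 − 10)/13.638 = 1.72, so A = 0.043. Enlarging raises the error.
- z1 = 1.5. Final 143: (23.63 − 15)/6.557 = 1.32, so A = 0.094. Final 286: (33.42 − 15)/13.638 = 1.35, so A = 0.088. Enlarging lowers it slightly.

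The inflation comes from enlarging after weak interim results.

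**4. Error under assumed rules, test on all data at 1.976.** The conditional-power (CP) rule enlarges until CP under the observed trend reaches 80% or the cap is met. The worst case picks, for each z1, the permitted increase that maximises A.

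| Interim per arm | Cap per arm | CP rule, no lower limit | Worst case |
|---|---|---|---|
| 100 | 215 | 0.0294 | 0.0304 |
| 100 | 286 | 0.0317 | 0.0331 |
| 120 | 215 | 0.0299 | 0.0314 |
| 120 | 286 | 0.0325 | 0.0346 |

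Larger caps give more: at 429 per arm and n1 = 100, 0.0343 and 0.0360. A simulation of 2,000,000 trials for n1 = 100, cap 286, gave 0.0316 for the CP rule.

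**5. Same CP rule with a minimum.** If an increase is allowed only when CP at the planned size is at least 20%, error is 0.0241-0.0244 (n1 = 100) and 0.0228-0.0233 (n1 = 120) over the same caps. At a 50% minimum it is 0.0241 and 0.0230-0.0231. There is no inflation.

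**6. Does ignoring the difference suffice?** Not with 1.976 unchanged, because that value belongs to a fraction of 0.70. With n1 = 100 and final sizes of 243, 286 or 486 chosen independently of the difference, error is 0.0264, 0.0267 or 0.0274. Simulated recalculation from the SD alone gave 0.0255 to 0.0268 for true SD 12 to 18. Solving the step 2 formula for total error 0.025 at 286 per arm moves the final value from 1.976 to about 2.01.

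**7. Fixed weights.** Using sqrt(0.7) × Z1 + sqrt(0.3) × Z2 with 2.628 and 1.976, error is 0.0250 whatever n2 is. The simulation in step 4 gave 0.0249 for this test under the same rule.

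**The case against.** Neither document says in words which test applies after a recalculation. That the all-data interval at 1.976 is kept is inferred from its being the only final test given. Recalculation is also optional, and some sensible difference-based rules cost nothing, as step 5 shows. An enlargement would not go unreviewed: Protocol 12 requires regulatory permission, Protocol 10.2 treats changes to statistical methods as significant amendments, and Protocol 9.7 requires deviations from the statistical plan to be justified.

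Most of this stands, and it limits the claim. A reader might infer that the 2.5% error is breached, or that it would be 3.5-4%. The documents support neither: they state no rule or cap, and figures that high need caps far above twice the planned size. What the objection does not do is protect the error rate. Regulatory permission and amendment review do not change the null distribution of the final statistic, and none of the harmless rules is written into the plan.

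**Conclusion.** The point holds as a missing guarantee. The plan allows recalculation from the interim treatment comparison, specifies no test that stays valid afterwards, and restricts the recalculation in no way. Under an 80% conditional-power rule with no lower limit and caps of 215-286 per arm, one-sided error is about 2.9-3.2% (worst case 3.0-3.3%) with the interim at 100 per arm. At 120 per arm it is about 3.0-3.3% (worst case 3.1-3.5%). A minimum conditional power of 20-50% removes the excess.

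These figures rest on three things: the assumed rules and caps, the inference that 1.976 is applied to all data, and a 2.5% target read from the boundaries, the 95% two-sided interval and N = 143 rather than from the text. If the plain 95% interval of Protocol 9.1.2 were used at the end, error would already be 0.0259 without any recalculation (interim at 70%).

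**What to change.** First reconcile two things. Settle the interim size (240 patients in the synopsis interim text and Protocol 9.2, 200 in Protocol 9.3 and the SAP), so that weights and boundaries match it. Then correct the stated one-sided error of 0.05 to agree with the boundaries, interval and sample size.

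Then, in the synopsis, Protocol 9.2 and SAP 11, replace the open-ended recalculation clause (adding it to the synopsis, which has none) with one pre-specified option:

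- **(a)** Recalculate only from the pooled SD of the haemoglobin change, computed without arm labels, and allow increases only. Recompute the final critical value from the alpha-spending function at the information fraction actually achieved, so that the total, including what was spent at the interim, is 2.5%.
- **(b)** If the observed difference may be used, compute the final statistic with stage weights fixed in advance from the planned information fraction: sqrt(0.7) and sqrt(0.3) for 100 of 143 per arm. Compare it with the matching final boundary, whatever the final size.

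Whichever is chosen, state the cap and who sees the interim results. The change is to wording only. Option (a) cannot react to the observed difference; option (b) loses a little efficiency if the trial is enlarged.

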## 9.3 Target number of the clinical trial subjects with the sample size justification

Calculation of the sample size is based on published works focusing on iron (III) hydroxide polymaltosate efficacy:

- 7) Maltofer Product Information leaflet (http://www.aspenpharma.com.au/product\_info/pi/PI\_Maltofer.pdf)
- 8) Santiago P. Ferrous versus ferric oral iron formulations for the treatment of iron deficiency: a clinical overview. Scientific World Journal. 2012;2012:846824.
- 9) Geisser P. Safety and efficacy of iron(III)-hydroxide polymaltose complex / a review of over 25 years' experience. Arzneimittelforschung. 2007;57(6A):439-52;

Based on the data of these publications, during 12-weeks of oral administration of iron (III) hydroxide polymaltosate the hemoglobin level can increase on average by 8-15 g/L with a standard deviation up to 15 g/L. As similar efficacy is expected in both groups, zero difference in primary efficacy parameter will be used for calculation of sample size. Maximum value of standard deviation was used -15 g/L to take a maximum variability of the primary endpoint variable into account for properly powered study.

The value of 5 g/L was selected as the non-inferior efficacy limit (in accordance with the limit stated and justified in the above mentioned works.

Thus, the following assumptions were proposed for calculations:

- 10) Changes in blood hemoglobin level (g/L) after 12-weeks of iron-deficiency anemia treatment (during the final visit), as compared with the baseline value (the screening visit 0) are expected to be similar for the investigational and reference drug groups (i.e. expected difference between the two groups is set to zero).
- 11) The pooled standard deviation for the changes in hemoglobin level was 15 g/L.
- 12) Non-inferiority margin is 5 g/L.
- 13) The significance level (two-sided, in accordance with FDA recommendations) is 95%, which corresponds to the type I one-sided error 0.05.
- 14) Power of the study is 80%, which corresponds to the type II error 0.20.
- 15) Statistical hypotheses evidence of a non-inferior efficacy:

- 16) The ratio between the study and control group sizes is 1:1
- 17) Interim analysis will be performed at 70% of the total sample size
- 18) O'Brien-Fleming alpha-spending function will be used with 80% power for efficacy boundary that will correspond to the following critical values for t-test: 2,628 for interim analysis (corresponds to p=0,005) and 1,976 for final analysis (corresponds to p=0,0245);

Calculation was performed using the clinfun package of Microsoft R Open software (available at https://mran.microsoft.com – Microsoft R Application network), that uses the group sequential design approach for the calculation of fixed sample sizes for the interim and final analysis. According to the output from the clinfun package, 143 subjects per group (286 subjects in total) should complete the study in order to confirm non-inferiority. 200 (100 per group) subjects should have evaluable data to perform interim analysis. Taking 15% withdrawal rate into account, one need to randomize 336 subjects (168 subjects per group). Taking 30% screening failure rate, up to 480 subjects should be screened to achieve target randomization.

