Examinations	
 
Baseline data (demography, past medical history and laboratory data) will be collected for all subjects at screening.
 
The parameters for the study therapy efficacy evaluation will be collected prior to treatment and after 12-weeks of treatment: 
 
Haemoglobin (complete blood count),
 
Iron metabolism parameters (serum ferritin, serum iron, transferrin, percent transferrin saturation).
 
 
 
Safety evaluation of the study therapy will be performed throughout the study and will be based on detection of any adverse events occurring during the study. The following will be performed:
 

	
 
Physical examination, including BP and heart rate measurement, and identification of complaints on digestive system disorders (at screening, during Visit 2 and the final visit).
 
Complete blood count (at screening and after 12-weeks of treatment),
 
Blood chemistry (at screening),
 
Urinalysis, pregnancy test (at screening),
 
Concomitant therapy recording (during each visit).
 
	
Statistical analysis	Efficacy evaluation:	
	Primary efficacy endpoint:	
	
 
Changes in blood haemoglobin level (g/L) after 12-weeks of iron-deficiency anaemia treatment (during the final visit), as compared with the baseline value (the screening visit) between the study groups.
 
Analysis of covariance (ANCOVA) will be used as the main method of assessment of the primary endpoint, with baseline haemoglobin value being a covariate and four fixed factors (treatment group, gender, weight and baseline Hb level (80–94 g/L vs 95–110 g/L). Unrestricted least significant differences (LSD) method will be applied to the ANCOVA results with the calculation of least-square (LS) means with 95% CI for LS means for the difference between the study groups. Non-inferiority will be confirmed if the upper limit of the two-sided 95% confidence interval for LS mean will not exceed the pre-defined non-inferiority margin of 5 g/L.
 
	
	Secondary efficacy endpoints:	

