	MedDRA SMQ for the corresponding symptoms), considered as
	related to the study therapy by the investigator, will be analyzed
	separately.
	Descriptive statistics will be used for presentation of the result.
	Comparison of all AE incidence between the study groups will be
	performed using the Fisher's exact test or chi-square test depending
	on the number of expected observations per cell (<5 or $\geq$ 5), and
	comparison of intensity (and possible causal relationship between the
	treatment received and the AE) will be performed using Cochrane-
	Armitage trend test for the ordered categorical data.
	3) Changes in laboratory test results (assessed in central laboratory)
	over time and frequency of abnormal test results (according to the
	normal ranges of central laboratory) will be summarized by group
	and also compared by group using corresponding tests for
	quantitative data and qualitative data (see below).
	4) Changes in vital signs over time and frequency of abnormal
	physical examination findings will be summarized by group and also
	compared by group using corresponding tests for quantitative data
	and qualitative data (see below). Quantitative data will be compared using the t test or Mann Whitney.
	Quantitative data will be compared using the t-test or Mann-Whitney test depending on the normality of the distribution (which will be
	tested using Shapiro-Wilk test).
	Qualitative data will be compared using the Fisher's exact test or chi-
	square test depending on the number of expected observations per
	square test depending on the number of expected observations per cell (<5 or $\geq$ 5).
Interim analysis	One formal Interim analysis to assess the primary and secondary
-	endpoints of efficacy is planned when the population of patients with
	• • •

	available primary efficacy endpoint data is at least 240 patients (120 patients in each group treatment: the main group is Ferrum Lek ® (iron (III) hydroxide polymaltosate) and the reference group MALTOFER ® (iron (III) hydroxide polymaltosate). Safety and Efficacy will be assessed for all patients who received at least one dose of the randomized treatment at the time of the interim analysis. Based on the results of the interim analysis of the primary and secondary statistical endpoints of the efficacy and safety of the study Sponsor may decide to stop the study if study endpoints have been met as per protocol based on the results of interim analyses.	

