2) The pooled standard deviation for the changes in hemoglobin level was 15 g/L.
3) Non-inferiority margin is 5 g/L.
4) The significance level (two-sided, in accordance with FDA recommendations) is 95%, which corresponds to the type I one-sided error 0.05.
5) Power of the study is 80%, which corresponds to the type II error 0.20.
6) Statistical hypotheses – evidence of a non-inferior efficacy:
H0: $\mu_{A} - \mu_{B} \le 5.0$ H1: $\mu_{A} - \mu_{B} > 5.0$
7) The ratio between the study and control group sizes is 1:1
8) Interim analysis will be performed at 70% of the total sample size

 
9) O'Brien-Fleming alpha-spending function will be used with 80% power for efficacy boundary that will correspond to the following critical values for t-test: 2,628 for interim analysis (corresponds to p=0,005) and 1,976 for final analysis (corresponds to p=0,0245);
 

Calculation was performed using the clinfun package of Microsoft R Open software (available at https://mran.microsoft.com – Microsoft R Application network), that uses the group sequential design approach for the calculation of fixed sample sizes for the interim and final analysis.
According to the output from the clinfun package, 143 subjects per group (286 subjects in total) should complete the study in order to

confirm non-inferiority. 200 (100 per group) subjects should have evaluable data to perform interim analysis. Taking 15% withdrawal rate into account, one need to randomize 336 subjects (168 subjects per group). Taking 30% screening failure rate, up to 480 subjects should be screened to achieve target randomization.
should be serected to achieve target randomization.

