#### 9.1.2 Analysis of the primary efficacy endpoint

#### Primary efficacy endpoint:

• Changes in blood haemoglobin level (g/L) after 12-weeks of iron-deficiency anaemia treatment (during the final visit), as compared with the baseline value (the screening visit) between the study groups.

Analysis of covariance (ANCOVA) will be used as the main method of assessment of the primary endpoint, with baseline haemoglobin value being a covariate and four fixed factors (treatment group, gender, weight and baseline Hb level (80–94 g/L vs 95–110 g/L). Unrestricted least significant differences (LSD) method will be applied to the ANCOVA results with the calculation of least-square (LS) means with 95% CI for LS means for the difference between the study groups. Non-inferiority will be confirmed if the upper limit of the two-sided 95% confidence interval for LS mean will not exceed the pre-defined non-inferiority margin of 5 g/L.

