- 2) A pooled standard deviation for the changes in hemoglobin levels was 15 g/L.
- 3) The non-inferiority margin is 5 g/L.
- 4) The significance level (two-sided, according to the recommendations by the Food and Drug Administration) is 95%, which corresponds to a one-sided type I error of 0.05.
- 5) The study power is 80%, which corresponds to a type II error of 0.20.
- 6) Statistical hypotheses are the demonstration of non-inferiority:

$$\mu A - \mu B > 5.0$$

- 7) The ratio between the test and control group sizes is 1:1.
- 8) The interim analysis will be conducted when 70% of the total sample size is reached.
- 9) The O'Brian-Fleming alpha-spending function will be applied with 80% power for the efficiency frontier, which will satisfy the following critical values of the t-test: 2.628 for the intermediate analysis (corresponding to p = 0.005) and 1.976 for the final analysis (corresponding to p = 0.0245).

STATISTICAL ANALYSIS PLAN

Calculations were performed using the clinfun package of the R software, in which the calculation of a fixed sample size for interim and final analyses was performed using the group sequential design.

According to the data obtained with the clinfun package, 143 subjects in each group (total: 286 subjects) should complete the study to confirm the hypothesis of non-inferiority. For the interim analysis, data for 200 subjects (100 in each group) that are suitable for analysis should be obtained. Taking into account the frequency of premature discontinuation of the study, which is 15%, it is necessary to randomize 336 people (168 people in each group). Taking into consideration the withdrawal rate based on the results of the screening that equals to 30%, about 480 people should undergo screening to achieve the target level of randomization.

3. General analysis values

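### The one-sided alpha is misprinted as 0.05 (the design uses 0.025), the interim trigger is 240 in two places and 200 in four, and the Protocol's flat 95% CI for the primary test conflicts with the SAP's look-dependent CI

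*Protocol*

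**What the plan says.** **Alpha.** Item 4 of the synopsis sample-size list and the corresponding item in Protocol 9.3 set a two-sided 95% level, "which corresponds to the type I one-sided error 0.05". SAP 2.3 repeats it: "which corresponds to a one-sided type I error of 0.05". The same lists give a margin of 5 g/L, SD 15 g/L, zero expected difference, 80% power, 1:1 allocation, a look at 70% of the sample, an O'Brien-Fleming alpha-spending function, critical values 2.628 (p=0.005) and 1.976 (p=0.0245), and 143 completers per arm.

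**Interim trigger.** The synopsis interim text and Protocol 9.2 run the interim when the number with "available primary efficacy endpoint data is at least 240 patients". The synopsis sample-size text and Protocol 9.3 say "200 (100 per group) subjects should have evaluable data to perform interim analysis". SAP 2.3 says "data for 200 subjects (100 in each group) that are suitable for analysis should be obtained", and SAP 11 says the interim group "will include at least 200 subjects".

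**Decision rule.** The synopsis states: "Non-inferiority will be confirmed if the upper limit of the two-sided 95% confidence interval for LS mean" stays within 5 g/L, and Protocol 9.1.2 uses the same criterion. Protocol 9.4 and SAP 3.1 put all tests at 95%/0.05. SAP 8.1 instead makes the CI percentage depend on whether the analysis is interim or final. It refers to clause 2.3 for the value, and that clause gives critical values and p-values but no percentage. Protocol 9.2 and SAP 11 both let the sponsor stop at the interim if the endpoints are met according to the protocol.

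**The concern.** A two-sided 95% level corresponds to a one-sided error of 0.025, so the printed assumption is wrong and leaves open which level the design was built on.

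The two trigger counts cannot both stand for the same look. The synopsis contradicts itself, and Protocol 9.2 contradicts Protocol 9.3.

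The decision rule matters most. Testing twice, each time against an unadjusted 95% CI, raises the chance of a false non-inferiority claim above 2.5%. The study is open-label (Protocol 4.4.2), the sponsor knows the allocation (Protocol 4.10), and the sponsor decides on stopping. A choice between two criteria made after the interim data are seen would be hard to defend.

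**Working it through.** **Inputs** (synopsis, Protocol 9.3, SAP 2.3): margin 5, SD 15, true difference 0, power 80%, looks at 0.70 and 1, boundaries 2.628/1.976, 143 per arm (286 in total), 336 randomized.

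**1. Which alpha gives 143 per arm?**
- Fixed design, n per arm = 2 × (15/5)² × (z_α + 0.8416)². One-sided 0.025: 18 × (1.960 + 0.8416)² = 141.3. One-sided 0.05: 18 × (1.645 + 0.8416)² = 111.3.
- The exponent implied by the printed boundaries is ln(2.628/1.976)/ln(1/0.7) = 0.799, so take the shape c × t^(−0.8).
- Solving that shape for one-sided 0.025 gives 2.628 at the interim and 1.976 at the final, with n = 142.1, hence 143. This reproduces the plan.
- Solving it for one-sided 0.05 gives 2.225/1.673 and n = 112.4, hence 113. This does not.
- By t, the one-sided tail of 2.628 on 198 df is 0.0046 and of 1.976 on 284 df is 0.0246. The printed p-values are therefore one-sided, though not labelled so.

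**2. Which trigger is 70%?** 200/286 = 69.9%. 240/286 = 83.9%. 240/336 = 71.4% of those randomized. Only 200 is 70% of the 286 completers on which the calculation rests.

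**3. What does each decision rule give?** The two test statistics are treated as bivariate normal with correlation √(100/143), or √(120/143) for an interim at 240. The drift with no true difference is 5/(15 × √(2/143)) = 2.819. The error rates do not depend on the SD.

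| Rule (interim / final) | One-sided error, look at 200 | Look at 240 | Power, look at 200 |
|---|---|---|---|
| Flat 95% CI, 1.96 / 1.96 | 3.78% | 3.44% | – |
| 2.628 / 1.96 | 2.59% | 2.52% | – |
| 2.628 / 1.976 | 2.50% | 2.43% | 80.2% (80.1% at 240) |
| p-values read as two-sided, 2.807 / 2.249 | 1.30% | – | 71.9% |

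**4. How often do the rules part at the interim?** With 100 per arm, SE = SD × √(2/100), and the chance of success with zero difference is Φ(5/SE − c).
- SD 15: SE = 2.121 and 5/SE = 2.357. The chance is Φ(0.397) = 65.4% with 1.96 and Φ(−0.271) = 39.3% with 2.628.
- SD 12 (an assumption; the documents say up to 15): SE = 1.697 and 5/SE = 2.946. The chances are 83.8% and 62.5%.
- The required point estimates differ by (2.628 − 1.96) × SE = 1.42 g/L at SD 15 and 1.13 g/L at SD 12, whichever way the difference is signed.

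**5. CI levels implied by the printed boundaries.** 2.628 gives 99.14% (normal) or 99.07% (t, 198 df). 1.976 gives 95.18% (normal) or 95.09% (t, 284 df).

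**6. The boundary's name.** The O'Brien-Fleming shape has exponent 0.5, which at a 70% look and one-sided 0.025 gives 2.400/2.008. The Lan-DeMets spending-function version gives 2.438/2.000. The printed pair is neither, although it controls the error. The phrase linking 80% power to the boundary suggests that 0.8 was entered as the shape parameter; that is an inference.

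**The case against.** The best defence is that the adjusted rule is already in the plan. The synopsis and Protocol 9.3 list 2.628 and 1.976, Protocol 9.1 defers to the SAP for the full analysis, and SAP 8.1 ties the CI level to the look. On that reading the error is 2.5%, and 3.8% is a worst-case misreading. This stands as a description of the likely intent. It does not remove the conflict. In the Protocol the critical values appear only among the sample-size assumptions, its only stated success criterion is the flat 95% CI, and both stopping texts point to the protocol. SAP 3.1 also still puts all tests at 0.05.

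Other objections carry some weight:
- Reading the p-values as two-sided is unlikely, because the critical values stand beside them: two-sided, 2.628 would be about 0.009 and 1.976 about 0.048. The missing label is a small defect.
- A look at 240 with the printed boundaries is harmless (2.43% error, 80.1% power), and 240 may have come from 70% of 336 = 235. The two counts must still be reconciled, and 200 agrees with the calculation and with both SAP statements.
- The boundary could instead be changed to fit its name. Keeping 2.628/1.976 leaves the design as calculated.
- Protocol 9.2 and SAP 11 allow sample-size recalculation from the interim results without a rule for the final critical value. The 2.5% figure therefore assumes no such recalculation.

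**Conclusion.** The concern holds. The printed one-sided 0.05 is a misprint: the design was calculated at 0.025 and N is correct. The trigger conflict is real, but by itself it neither changes N nor inflates the error. The consequential defect is that the primary non-inferiority criterion has two incompatible versions at a look where the trial can stop. The Protocol's literal rule gives a one-sided error of 3.8% (3.4% with the look at 240), against 2.5% under SAP 8.1 with the printed critical values. At SD 15 and no true difference, interim success is 65% under one rule and 39% under the other. Almost all of the excess comes from the interim: using 1.96 instead of 1.976 at the final look alone moves the error only from 2.50% to 2.59%.

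These figures assume normal test statistics, the unadjusted SD of the plan's own calculation (for power and interim chances only), and no sample-size recalculation. The boundary name is a labelling error.

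**What to change.** - State one-sided alpha 0.025 in the synopsis, Protocol 9.3 and SAP 2.3.
- Use one trigger everywhere: 200 patients with Week 12 hemoglobin, 100 per arm, 70% of 286. The places to align are both synopsis texts, Protocol 9.2 and 9.3, and SAP 2.3 and 11.
- Define the primary CI identically in the synopsis, Protocol 9.1.2 and SAP 8.1: LS-mean difference ± 2.628 SE at the interim (about 99.1%) and ± 1.976 SE at the final (about 95.1% by t, 95.2% by normal).
- Label the p-values one-sided and make them agree with the critical values (about 0.0046 and 0.0246 by t).
- Exempt the primary test from the general 95%/0.05 sentences in Protocol 9.4 and SAP 3.1.
- Drop the O'Brien-Fleming name and keep the printed boundary.

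The cost is wording in the Protocol and SAP. The 143 per arm, the 336 randomized and the boundaries 2.628/1.976 stay. The change should be made before any interim data are seen.
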